4.1.1. Screening

Participants will be screened for eligibility for up to 6 weeks during the Screening Period. For participants in the LN cohort, all screening laboratory assessments should be performed as soon as possible after signing of the informed consent form (ICF). All participants in the LN cohort should be randomized as soon as possible once eligibility is confirmed.

4.1.2. Blinded Initial Evaluation Period

Approximately 126 adult participants with either LN or IgAN will be randomized into the study on Day 1 (approximately 70 participants in the LN cohort and approximately 56 participants in the IgAN cohort), as follows:

- For each disease cohort, participants meeting eligibility criteria will be randomly
 assigned in a 3:1:3 ratio to receive ALXN2050 180 mg bid, ALXN2050 120 mg bid,
 or placebo bid (Table 8).
- For the IgAN cohort, participants assigned to the placebo group will also be assigned
 to their study treatment for the Blinded Extended Treatment Period (ALXN2050
 180 mg bid or ALXN2050 120 mg bid) in a 1:1 allocation ratio at the time of
 randomization.

Table 8: Summary of Participants in Each Treatment Group During the Blinded
Initial Evaluation Period

Treatment Group	LN Cohort	IgAN Cohort	
	Approximate Number of Participants	Approximate Number of Participants	
ALXN2050 180 mg bid	30	24	
ALXN2050 120 mg bid	10	8	
Placebo bid	30	24	

Abbreviations: bid = twice daily; IgAN = immunoglobulin A nephropathy; LN = lupus nephritis

Stratification will be performed as follows:

- For the LN cohort: by whether corticosteroid induction treatment was initiated prior to Screening versus during the Screening Period.
- For the IgAN cohort: by mean proteinuria (1 to 2 g/day versus > 2 g/day) from 2 valid 24-hour urine collections during the Screening Period.

After completion of the Day 1 Visit assessments, participants will receive the first dose of study intervention prior to leaving the clinic. Participants will continue to receive bid doses of study intervention throughout the Blinded Initial Evaluation Period (Table 11).

4.1.3. Blinded Extended Treatment Period

After completion of the Blinded Initial Evaluation Period (Week 26 Visit), participants will continue to receive study intervention during a Blinded Extended Treatment Period for 24 weeks as follows:

- Participants in the LN cohort will continue to receive their randomized allocation of study intervention (ALXN2050 180 mg, ALXN2050 120 mg, or placebo) bid. After Week 26, additional standard of care therapy for participants with Suboptimal Response is allowed at the clinical discretion of the Investigator in conversation with the Medical Monitor.
- Participants in the IgAN cohort randomized to active treatment will continue to receive their randomized allocation of study intervention (ALXN2050 180 mg or ALXN2050 120 mg) bid.

 Participants in the IgAN cohort randomized to the placebo group will receive either ALXN2050 180 mg bid or ALXN2050 120 mg bid as assigned at the time of randomization.

4.1.4. Open-label Extension Period

After completion of all assessments at the end of the Blinded Extended Treatment Period (Week 50 Visit), all participants will have the opportunity to enter an OLE Period and receive ALXN2050 for up to 2 years (104 weeks) if no relevant side effects (in the opinion of the Investigator) and no Treatment Failure (LN cohort) are present. During the OLE Period:

- Participants in the LN cohort randomized to the active treatment groups will continue to receive the same dosing regimen as assigned during the Blinded Extended Treatment Period.
- Participants in the LN cohort randomized to the placebo group will no longer receive
 placebo and will continue to receive allowed concomitant therapy alone. These
 participants will have the option to receive ALXN2050 180 mg bid or the optimal
 dose (if already identified) if the participant has a Renal Flare as defined in
 Section 8.1.6 or Suboptimal Response as defined in Section 8.1.8.
- Participants in the IgAN cohort will continue to receive the same dosing regimen as assigned during the Blinded Extended Treatment Period.
- Participants in both cohorts receiving ALXN2050 who complete at least 50 weeks of treatment will receive the optimal dose level of ALXN2050 (180 mg or 120 mg bid) once an optimal dose is identified based on results of the primary analysis at Week 26 and/or Data Monitoring Committee (DMC) review of the safety and efficacy data.
- Percentage change in proteinuria from baseline and change from baseline in eGFR at Weeks 102 and Week 154 will be assessed as exploratory efficacy endpoints. Safety and tolerability will also be evaluated continually throughout the OLE Period.

After completion of the study or after ED, a Safety Follow-up Visit will be conducted 30 days after the last dose of study intervention.

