After completion of all assessments at the end of the Blinded Extended Treatment Period (Week 50 Visit), all participants will have the opportunity to enter the Open-label Extension (OLE) Period for up to 2 years (104 weeks) if no relevant side effects (in the opinion of the Investigator) are present.

During the OLE Period:

- Participants in both cohorts receiving ALXN2050 during the Blinded Initial
 Evaluation Period and the Blinded Extended Treatment Period will continue their
 active treatment at the same dose level. Once an optimal dose is identified (based on
 the 26 weeks primary analysis) for each cohort, all participants in that cohort with at
 least 50 weeks of study treatment will receive the optimal dose of ALXN2050.
- Participants in the LN cohort randomized to the placebo group will no longer receive
 placebo and will continue to receive allowed concomitant therapy. These participants
 will have the option to receive ALXN2050 180 mg bid or the optimal dose (if already
 identified) if the participant has a Renal Flare as defined in Section 8.1.6 or
 Suboptimal Response as defined in Section 8.1.8.
- Percentage change in proteinuria from baseline and change from baseline in eGFR at Weeks 102 and Week 154 will be assessed as exploratory efficacy endpoints. Safety and tolerability will also be evaluated continually throughout the OLE Period.

Disclosure Statement: This is a parallel-group treatment study with 3 arms that is participant and Investigator blinded during the 26-week Blinded Initial Evaluation Period and the 24-week Blinded Extended Treatment Period.

Number of Participants:

Approximately 70 participants in the LN cohort and approximately 56 participants in the IgAN cohort will be randomly assigned to study intervention.

Intervention Groups and Duration:

The study consists of an up to 6-week Screening Period, a 26-week Blinded Initial Evaluation Period, a 24-week Blinded Extended Treatment Period, and an OLE Period of up to 2 years. In addition, all participants will be followed for safety for 30 days after the last dose of study intervention. Thus, the total treatment duration is 154 weeks, and the total study duration is up to 164 weeks.

Data Monitoring Committee: Yes

Ethical Considerations and Benefit-Risk Assessment

This study will be conducted as specified in this protocol and in accordance with the following:

[figure not shown]

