8.1.6. Renal Flare (LN Cohort Only)

Renal Flare is determined in the opinion of the Investigator in addition to the criteria outlined below:

- For participants who achieve CRR (Section 8.1.10), a Renal Flare is the reproducible recurrence of proteinuria ≥ 1 g/g
- For all other participants, a Renal Flare is either of the following:
 - Reproducible increase of serum creatinine > 25% higher than baseline or above the ULN, plus any one of the following:
 - Reproducible proteinuria ≥ 75% higher than baseline
 - Worsening active urinary sediment compared to baseline as defined by an increase of ≥ 5 RBCs/hpf or new RBC casts (based on local laboratory results from at least 2 samples)
 - Kidney biopsy demonstrating LN Class III or IV activity which was conducted since the biopsy used for eligibility
 - Reproducible doubling of the UPCR from a 24-hour urine collection compared with the lowest previous value obtained after the first dose of study intervention.
- Reproducibility of proteinuria requires that UPCR from the morning spot urine collection is confirmed by a central lab UPCR based on 24-hour urine collected within 2 weeks.
- Reproducibility of serum creatinine requires 2 blood tests within a 2 week period.

Participants who meet criteria for the protocol-defined Renal Flare will receive additional standard of care therapy (Section 6.5.4). The Medical Monitor should be notified of the Renal Flare by the Investigator or Sub-investigator.

Any Renal Flare that does not meet the protocol-defined Renal Flare criteria may be treated with a limited duration of increased oral corticosteroids (≤ 14 days) after discussion with the Medical Monitor. Such treatment will not be considered additional standard of care therapy and will not be considered Treatment Failure.

Renal Flare criteria will be recorded on the Renal Flare eCRF.

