8.1.8. Suboptimal Response (LN Cohort Only)

A Suboptimal Response is determined in the opinion of the Investigator in addition to the following criterion after the Week 26 Visit:

 Reproducible proteinuria ≤ 25% decreased compared to baseline based on UPCR on a 24-hour urine collection performed by central laboratory

Reproducibility of proteinuria requires that the proteinuria based on a UPCR from a spot urine collection is confirmed by a central laboratory UPCR calculated on a 24-hour urine collection obtained within a 2-week period.

Participants with Suboptimal Response must be discussed with the Investigator and Medical Monitor. Participants with Suboptimal Response will stay in the study and continue to receive study intervention. Intensification of current standard of care or introduction of new immunosuppressive therapies are allowed per the clinical discretion of the Investigator in conversation with the Medical Monitor and will be considered additional standard of care therapy.

Participants with Suboptimal Response will be included as Treatment Failure.

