8.1.9. Treatment Failure (LN Cohort Only)

Treatment Failure is defined as the receipt of additional standard of care therapy at any time during the study for protocol defined Renal Flare, severe Extrarenal SLE Flare, or Suboptimal Response.

Increase in corticosteroids for Extrarenal SLE Flare not meeting the protocol definition of severe Extrarenal SLE Flare, Renal Flare not meeting protocol definition for Renal Flare, lack of response not meeting the protocol definition of Suboptimal Response, other medical conditions, or surgery limited to \leq 14 days duration are not included in Treatment Failure.

Participants who meet the criteria for Treatment Failure may continue to receive the study intervention and stay in the study. If a participant has 2 Treatment Failures, study intervention discontinuation should be considered (Section 7.1). If a CNI is used for additional standard of care therapy, study intervention will need to be discontinued 3 days prior to CNI administration.

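### The protocol gives two different rules for LN entry to the open-label extension, and Section 4.1.4 is unclear against its own placebo option

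*Protocol*

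**What the plan says.** Two places in the protocol state who may enter the OLE after the Week 50 Visit. Section 4.1.4 sets two conditions: entry is open "if no relevant side effects (in the opinion of the Investigator) and no Treatment Failure (LN cohort) are present". The OLE paragraph of the synopsis (Section 1.1) sets one: "if no relevant side effects (in the opinion of the Investigator) are present".

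Further down Section 4.1.4, in the list of what happens during the OLE, the bullet on LN participants randomized to placebo says that these "participants will have the option to receive ALXN2050 180 mg bid or the optimal" dose if they have a Renal Flare or a Suboptimal Response. It does not say when the event must have arisen.

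Three other sections decide who counts as a Treatment Failure:

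- Section 8.1.9: "Treatment Failure is defined as the receipt of additional standard of care therapy at any time during the study", given for a protocol-defined Renal Flare, a severe Extrarenal SLE Flare or a Suboptimal Response.
- Section 8.1.6: "Participants who meet criteria for the protocol-defined Renal Flare will receive additional standard of care therapy".
- Section 8.1.8: "Participants with Suboptimal Response will be included as Treatment Failure". The same section leaves the additional therapy itself to the Investigator's discretion, in conversation with the Medical Monitor.

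On what follows a Treatment Failure, Section 8.1.9 says "Participants who meet the criteria for Treatment Failure may continue to receive the study intervention and stay in the study", and Section 8.1.8 says "Participants with Suboptimal Response will stay in the study and continue to receive study intervention". Section 7.1 lists two Treatment Failures, not one, among the reasons to consider stopping study intervention.

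**The concern.** A site applying Section 4.1.4 and a site applying the synopsis can reach opposite decisions on the same LN participant. The decision governs up to 104 weeks of open-label treatment and whether that participant contributes long-term safety data. Under 4.1.4 the LN extension holds only participants without a Treatment Failure; under the synopsis it holds both kinds. If practice is mixed, the Week 102 and Week 154 summaries of observed data describe a population that nobody has defined.

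For a placebo participant whose Renal Flare or Suboptimal Response came before Week 50, Section 4.1.4 can be read both ways. The entry sentence may refuse that participant, while the bullet appears to offer the drug because of the same event. For Suboptimal Response the reading also depends on which definition of Treatment Failure is applied, because 8.1.8 and 8.1.9 differ.

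**Working it through.** The plan states no figure on this point, so the check is mainly a comparison of texts.

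**Step 1. Apply each entry rule to the same LN participant.** Assume that the participant reaches Week 50 without relevant side effects, and that a failure earlier in the study still counts at entry. Section 4.1.4 does not settle the second assumption.

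| History before Week 50 | Section 4.1.4 | Synopsis |
|---|---|---|
| No flare, no Suboptimal Response, no additional therapy | Enters | Enters |
| Protocol-defined Renal Flare (8.1.6 requires additional therapy, so Treatment Failure under 8.1.9) | Refused | Enters |
| Severe Extrarenal SLE Flare (treated, by definition) | Refused | Enters |
| Suboptimal Response, additional therapy given | Refused | Enters |
| Suboptimal Response, no additional therapy | Refused under 8.1.8; enters under 8.1.9 | Enters |

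The two rules agree only in the first row. In the last row, 4.1.4 gives no single answer because 8.1.8 counts every Suboptimal Response while 8.1.9 requires that therapy was received.

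**Step 2. Add the placebo bullet.** An event that first arises during the OLE causes no conflict: the participant entered without a failure and the bullet then applies. For a Renal Flare or Suboptimal Response before Week 50, the entry sentence and the bullet can point in opposite directions, and nothing limits the bullet to new events.

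**Step 3. Trace the effect on the analyses.**

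- Week 26 and Week 50 data are collected before OLE entry, so neither rule touches them.
- For Weeks 102 and 154, SAP 4.4.1 and 4.4.2 reuse the models of SAP 4.3.1.1 and 4.3.1.3, which set data after intercurrent events to missing. SAP Table 6 lists additional therapy for a renal flare or suboptimal response as such an event. The sample code in SAP 6.4.2 carries the value at the event forward instead. Either way, OLE values after that therapy do not drive the model estimates, whichever entry rule applied.
- Two groups remain exposed in the models: participants treated for a severe Extrarenal SLE Flare, which Table 6 does not list, and participants with an untreated Suboptimal Response, who have no intercurrent event and whose OLE values would be used if they were admitted.
- Observed-data summaries and OLE safety tables depend directly on who was admitted.
- Disposition in SAP 6.2.1 is given by period with reasons for discontinuation, but asks for no count of participants kept out of the OLE by Treatment Failure.

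**Step 4. Illustrate the size.** Arm sizes of 30, 10 and 30 (180 mg, 120 mg, placebo) and 10% dropout come from Protocol 9.2. At Week 50 that leaves 30 × 0.9 = 27, 10 × 0.9 = 9 and 27, or 63 in all, with a placebo share of 27/63 = 43%. The synopsis rule admits up to 63. Under 4.1.4 the expected number per arm is n × (1 − Treatment Failure rate). The rates below are assumptions; the documents give none.

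| Assumed rate, active / placebo | Left: 180 mg / 120 mg / placebo | Total | Placebo share |
|---|---|---|---|
| 10% / 10% | 24.3 / 8.1 / 24.3 | 56.7 | 43% |
| 30% / 30% | 18.9 / 6.3 / 18.9 | 44.1 | 43% |
| 10% / 30% | 24.3 / 8.1 / 18.9 | 51.3 | 37% |
| 20% / 40% | 21.6 / 7.2 / 16.2 | 45.0 | 36% |

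Any non-zero rate changes who enters. The balance between arms moves only where the rates differ by arm.

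**The case against.** The strongest reply is that only one pair of statements conflicts directly, 4.1.4 and the synopsis, and that the rest can be read consistently. Much of this stands.

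- A reader might infer that 8.1.8, 8.1.9 and 7.1 admit participants with Treatment Failure to the OLE. They do not say so. None of them names the OLE, and a participant could stay on study intervention through Week 50 after one failure and still face a stricter condition for an optional extension. They are indirect support only.
- The silence of SAP 1.2 on Treatment Failure shows nothing, because that section gives no entry conditions at all and omits side effects too.
- The placebo bullet is listed among events during the OLE, and Table 5 of the protocol schedules monitoring for flare and Suboptimal Response there. Read as covering new events only, it fits the entry sentence. What remains is that the bullet does not say this.
- A reader might infer that every placebo participant with a Suboptimal Response between Weeks 26 and 50 is shut out. Under 8.1.9 that holds only if additional therapy was given, and for Suboptimal Response it is discretionary.
- A reader might infer that 4.1.4 removes more placebo than drug participants, and try to size this from the LN planning assumptions. With Week 26 to baseline ratios g of 0.60 (placebo) and 0.40 (180 mg) and a log SD of 0.60, the share with a fall in proteinuria of 25% or less is 1 − Φ((ln 0.75 − ln g)/0.60): 1 − Φ(0.372) = 35.5% and 1 − Φ(1.048) = 14.7%. The arithmetic is right, but these are not Treatment Failure rates. They assume the planned drug effect, borrow an SD from an IgAN source, and leave out Investigator opinion, confirmation by a 24-hour collection, timing after Week 26 and receipt of therapy.

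**Conclusion.** The point holds as a contradiction between Section 4.1.4 and the synopsis, both current text, together with an unresolved reading within 4.1.4 for placebo events before Week 50 and a mismatch between 8.1.8 and 8.1.9 on untreated Suboptimal Response. It affects access to the OLE, the LN long-term safety population and the observed-data Week 102 and 154 summaries, which are exploratory. A claim that the Week 102 and 154 treatment-sequence comparisons are biased would go too far, given how the SAP models handle data after additional therapy.

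The number of participants affected cannot be derived from the documents. On the assumed rates shown, between about 6 and 19 of 63 LN participants would be refused under 4.1.4 (63 − 56.7 = 6.3; 63 − 44.1 = 18.9). An imbalance between arms is plausible if the drug works, but it is not established. The dosing pause recorded in SAP Section 1 may lower the number further. The point is worth correcting because the change is cheap, but it does not threaten the main results.

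**What to change.** In the protocol:

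1. Reconcile Section 4.1.4 and the synopsis into one OLE entry rule for LN. Whether Treatment Failure bars entry is a clinical decision for the sponsor.
2. Align 8.1.8 with 8.1.9 on whether a Suboptimal Response without additional therapy is a Treatment Failure.
3. State how the entry rule fits the placebo option when the Renal Flare or Suboptimal Response arose before Week 50, and, if Treatment Failure bars entry, whether an earlier failure that has since resolved still counts.

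In the SAP, add to the disposition table (6.2.1) the number of LN participants who did not enter the OLE, by arm and reason, with Treatment Failure as a named reason.

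The cost is protocol wording and one extra table row. No primary or Week 50 analysis changes.

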4.1.5. Remote Visit Options in Times of Emergency

To ensure participant safety and treatment continuity in times of emergency (eg, COVID-19 pandemic), the following will apply where participants are not able to reach the study sites, and until participants are able to resume study visits at the site.

Remote visit options may be available at the Investigator's discretion and oversight, in accordance with the local regulations. Remote visit options may include visits conducted at the participant's home, an alternative qualified healthcare facility, or virtually through phone or video conference. All assessments for the study visit day should be conducted according to the SoA (Section 1.3), whenever possible. Information about adverse events (AEs), concomitant medications, allowed concomitant therapies, and disease-related signs or symptomatology must be sent to the Investigator for evaluation on the day of the remote visit. In case of any signs or symptoms indicating a serious adverse event (SAE), the participant will need to be evaluated at the study site.

4.2. Scientific Rationale for Study Design

Justification for specific design elements is provided in Table 9.

Table 9: Scientific Rationale for the Design of Study ALXN2050-NEPH-201

Design Element	Rationale
Target populations	Glomerular diseases such as LN and IgAN continue to respond poorly to treatment, resulting in CKD over time. While there has been some progress in terms of approved treatments with 2 recent approvals in some countries for patients with LN (ie, belimumab and voclosporin) and IgAN (budesonide), there remains a significant unmet need for novel interventions which would allow more definitive treatments for LN as well as disease-specific treatments for patients with IgAN, particularly in patients who are at risk of progressive kidney disease. See Section 2.2.3 and Section 2.2.4.
Randomized, double-blind, placebo-controlled	A randomized, double-blind, placebo-controlled study design in addition to allowed concomitant therapy consistent with the standard of care is selected to provide the most robust evidence of the efficacy of ALXN2050 on clinical response, disease progression, and safety. Randomization minimizes the effects of baseline differences and confounding factors on the study endpoints. The use of a placebo comparator allows for the true treatment effect of ALXN2050 by minimizing the risk of selection bias.
Randomization stratum	A single randomization stratum was selected for each cohort to ensure equal distribution of baseline characteristics that may impact the endpoints. See Section 6.3.1.
Selection of 2 dose levels (ALXN2050 180 mg bid and ALXN2050 120 mg bid)	The optimal dose of ALXN2050 in glomerular diseases is not known. Thus, participants will be randomized to a high-dose group (180 mg bid), a low-dose group (120 mg bid), or a placebo group in a 3:1:3 allocation ratio. The primary analysis will compare the high-dose treatment group to the placebo treatment group. A smaller number of participants will be randomized to the low-dose treatment group to collect supportive data that will be summarized descriptively. Given the unknown degree of AP inhibition required to achieve clinical efficacy in these indications and to ensure robust AP inhibition in a majority of patients, 180 mg bid was chosen for the high-dose group. See Section 4.3.
Primary endpoint (proteinuria)	Change in proteinuria is considered a valid surrogate endpoint for kidney survival in glomerular diseases. See Section 4.2.1.
Safety endpoints	The safety parameters being evaluated are commonly used in clinical studies per ICH and GCP guidelines.

Table 9: Scientific Rationale for the Design of Study ALXN2050-NEPH-201

Design Element	Rationale
Duration of study	The 26-week initial treatment duration provides adequate time to assess the safety and efficacy endpoints to demonstrate proof of concept for both cohorts in a Phase 2 study.
	The Extended Treatment Period and OLE Period will facilitate collection of longitudinal efficacy and additional safety data of ALXN2050 for all participants.

Abbreviations: AP = alternative pathway; bid = twice daily; CKD = chronic kidney disease; GCP = Good Clinical Practice; ICH = International Council for Harmonisation of Technical Requirements for Pharmaceuticals for Human Use; IgAN = immunoglobulin A nephropathy; LN = lupus nephritis; OLE = Open-label Extension

